#### See Section 5.0 for Dose Modifications based on Toxicities.

The therapy delivery maps (TDMs) for levofloxacin therapy are on the next 2 pages.

Prophylactic Therapy Delivery Map – AL Patients in Arm B	
Patients undergoing treatment for AL receive antibacterial prophylaxis during 2 consecutive cycles	
of chemotherapy.	Patient name or initials
	DOD

For each of 2 consecutive chemotherapy cycles, begin study treatment on Day 3 of systemic chemotherapy. Extensive details are in Section 4.0 (treatment overview). Cvcle: 1

This Therapy Delivery Map is on **one** (1) page.

		(-) F8-1		-,	
DRUG	ROUTE	DOSAGE	DAYS	IMPORTANT NOTES	OBSERVATIONS
Levofloxacin	PO*/IV  *Given PO if tolerated; otherwise by IV.	Age ≥ 6 months to < 5 years: 10 mg/kg twice daily ≥ 5 yrs: 10 mg/kg once daily	Daily beginning on Day 3 of systemic chemotherapy)^	^Continue until ANC is > 200/μL and rising post-nadir or Day 60 (from Day 1 of each cycle of systemic chemotherapy) if ANC > 200/μL is not reached or the day prior to the next cycle of chemotherapy.  Note age-based dosing	
 
a. History, physical, ht/wt, performance status
 
b. CBC, Cr (at intervals according to good patient care)
 
c. Optional peri-rectal swab or stool specimen (see Section 7.2)
 
† Infection information during infection observation period (see Section 7.1.2)
 

				Maximum per day: 500 mg if < 5 years of age, 750 mg if ≥ 5 years See Section 4.2 for rounding of oral doses	OBTAIN OTHER STUDIES AS REQUIRED FOR GOOD PATIENT CARE

		Htcr	n Wtkg	BSA	$_{\rm m}^2$	
Start Day	Stop Day Date	Age: $\geq$ 6 months to $\leq$ 5 years	Age: $\geq 5$ years	Studies †	Comments (Include any held doses, or dose modifications)	
Date (d/m/y)	(d/m/y)	LEVO^	LEVO^			
` **	• • • • • • • • • • • • • • • • • • • •	mgmg	mg			
		Enter calculated dose above an	d actual dose administered b	oelow		
0-3				a, b, c		
3 ( / / )	(_/_/)^	mgmg	mg			
(_/_/)	(_/_/)^	mgmg	mg			
(_/_/)	(_/_/)^	mgmg	mg			
(_/_/)	(_/_/)^	mgmg	mg			
Continue until ANC is > 200/uL and rising post-padir  ; see Section 4.1 for details regarding starting and stopping of levofloxacin						

Continue until ANC is  $> 200/\mu$ L and rising post-nadir'; see Section 4.1 for details regarding starting and stopping of levofloxacin. Levofloxacin should be discontinued immediately for any patient with confirmed tendinopathy (tendinitis or tendon rupture) (see Section 4.1).

On the TDM, indicate each start and stop dates of levofloxacin. The subject may start and stop levofloxacin multiple times prior to meeting the criteria for completion of levofloxacin. Levofloxacin should be held when parenteral antibiotics are administered for other indications such as for empiric or therapeutic management of infection.

See Section 5.0 for Dose Modifications for Toxicities and the COG Website posted materials for Supportive Care Guidelines

Prophylactic Therapy Delivery Map – HSCT Patients in Arm B	
Patients undergoing HSCT receive antibacterial prophylaxis during 1 transplant procedure.	Patient name or initials
	DOB

Begin study treatment on Day -2 from stem cell infusion. Extensive details are in Section 4.0 (treatment overview).

This Therapy Delivery Map is on one (1) page.

DRUG	ROUTE	DOSAGE	DAYS	IMPORTANT NOTES	OBSERVATIONS
Levofloxacin	PO*/IV	Age	Daily beginning on	^Continue until ANC is $> 200/\mu L$	a. History, physical, ht/wt, BSA, performance
		$\geq$ 6 months to $\leq$ 5 years:	Day -2^	and rising post-nadir or HSCT	status
	*Given PO if	10 mg/kg twice daily		Day +60 if ANC > $200/\mu$ L is not	b.CBC, Cr (at intervals according to good
	tolerated;			reached	patient care)
	otherwise by IV.	≥ 5 yrs: 10 mg/kg once daily		Note age-based dosing	c. Optional peri-rectal swab or stool specimen (see Section 7.2)
				Maximum per day: 500  mg if < 5  years of age, $750 \text{ mg if} \ge 5 \text{ years}$	† Infection information during infection observation period (see Section 7.1.2)
				See Section 4.2 for rounding of oral doses	OBTAIN OTHER STUDIES AS REQUIRED FOR GOOD PATIENT CARE

		Ht	_cm	Wtkg	BSA	$m^2$
Start Day	Stop Day Date	Age: $\geq$ 6 months to	< 5 years	Age: ≥ 5 years	Studies †	Comments (Include any held doses, or dose modifications)
Date (d/m/y)	(d/m/y)	LEVO^		LEVO^		
` • •		mg	mg	mg		
		Enter calculated dos	e above and	actual dose administered	l below	
-3					a, b, c	
-2 # (_ /_ /)	_ (_ /_ /)^	mg	mg	mg		
	_ (_ /_ /)^	mg	mg	mg		
	_ (_ /_ /)^	mg	mg	mg		
(_/_/)	_ (_ /_ /)^	mg	mg	mg		
	Continue until ANC is $> 200/\mu$ L and rising post-nadir ^ ; see Section 4.1 for details regarding starting and stopping of levofloxacin.					
	Levofloxacin should be discontinued immediately for any patient with confirmed tendinopathy (tendinitis or tendon rupture) (see Section 4.1).					

#Stem cell infusion 2 days later on Day 0

On the TDM, indicate each start and stop dates of levofloxacin. The subject may start and stop levofloxacin multiple times prior to meeting the criteria for completion of levofloxacin. Levofloxacin should be held when parenteral antibiotics are administered for other indications such as for empiric or therapeutic management of infection.

See Section 5.0 for Dose Modifications for Toxicities and the COG Website posted materials for Supportive Care Guidelines

## 5.0 DOSE MODIFICATIONS FOR TOXICITIES

For any patient with signs or symptoms suggestive of a possible tendon rupture, levofloxacin will be discontinued immediately. See Section 7.1.3 for required musculoskeletal follow-up assessments.

The dose of levofloxacin should be modified for impaired renal function as follows:

Patient Age	CrCl (mL/min/1.73m  )	Dose	
	>50	10 mg/kg q12h	
6 months to 4.99 years	20 - 50	5 mg/kg q12h	
	CrCl <20	NONE	
	>50	10 mg/kg q24h	
≥ 5 years	20 - 50	5 mg/kg q24h	
	CrCl <20	NONE	

## 6.0 DRUG INFORMATION

See the consent document for toxicities. All other information is available on the COG website in the commercial agent monographs manual titled "Drug Information for Commercial Agents used by the Children's Oncology Group." This manual is provided under Standard Sections for Protocols at: https://members.childrensoncologygroup.org/prot/reference materials.asp.

#### 7.0 EVALUATIONS/MATERIAL AND DATA TO BE ACCESSIONED

All baseline studies must be performed prior to starting protocol therapy unless otherwise indicated below.

Timing of protocol therapy administration, response assessment studies, and surgical interventions are based on schedules derived from the experimental design or on established standards of care. Minor unavoidable departures (up to 72 hours) from protocol directed therapy and/or disease evaluations (and up to 1 week for surgery) for valid clinical, patient and family logistical, or facility, procedure and/or anesthesia scheduling issues are acceptable per COG administrative Policy 5.14 (except where explicitly prohibited within the protocol).

# 7.1 Required & Optional Clinical, Laboratory and Disease Evaluations

# Obtain prior to start of phase unless otherwise indicated.

STUDIES TO BE OBTAINED	Baseline 	Infection	Late MSK
		Observation	Monitoring Period
		Period	
History, Demographic & Clinical Information	X		
Ht, Wt	X		
Performance Status	X		
CBC, Creatinine 	X		
Musculoskeletal Assessment	X		X
Infection Information		X	
Sterile Site Culture 		X	
Optional Peri-Rectal Swab or Stool Specimen 	X	X	

Baseline assessment will take place on Day 0-3 of the first cycle of chemotherapy on study for AL patients and between Day -5 and Day -3 from stem cell infusion for transplant patients.

This table only includes evaluations necessary to answer the primary and secondary aims. Obtain other studies as indicated for good clinical care. See Section 11.4 for routine AE reporting guidelines.

## 7.1.1 History, Demographic and Clinical Information

Demographic and clinical information collected at baseline will include age, sex, performance status, Down syndrome, ethnicity, height, weight, and episodes of bacteremia in the month prior and receipt of antibacterial therapy (not PCP prophylaxis) within 7 days prior to enrollment. Other information collected will include type of malignancy, relapse status, and chemotherapy information. For HSCT recipients, information collected will include donor type, degree of match for allogeneic recipients, stem cell source, conditioning regimen and graft-versus-host disease (GVHD) prophylaxis.

# 7.1.2 Infection Observation Period and Infection Information

The observation period for infectious outcomes, including the primary endpoint will be the same for both arms irrespective of whether the child discontinues levofloxacin early for those allocated to that arm. Specifically for patients receiving chemotherapy, the infection observation period will begin Day 3 of each cycle of chemotherapy and will end when the ANC is  $> 200/\mu L$  and rising post nadir, or at Day 60 (from Day 1 of each cycle of systemic chemotherapy) if an ANC of  $> 200/\mu L$  has not been reached, or Day 1 of the next cycle of chemotherapy, whichever occurs first. For patients undergoing HSCT, the observation period will begin on Day -2 from stem cell infusion and end when the ANC is  $> 200/\mu L$  and

<sup>2 To be done at intervals according to good patient care.

<sup>3 See Section 7.2. for collection details and Section 13.0 for shipping details.

rising post nadir, or at HSCT Day +60 if an ANC >  $200/\mu$ L has not been reached or the first day of subsequent cancer therapy, whichever occurs first.

## 7.1.2.1 General Infection Information

Data to be collected during the infection observation period will include incidence of fever with neutropenia, days of neutropenia, use of granulocyte-colony stimulating factor (G-CSF) and corticosteroid exposure (categorized as no exposure, ≤ 5 sequential days of or > 5 sequential days of corticosteroid treatment), incidence of signs or symptoms of tendinopathy (tendonitis or tendon rupture), incidence of fever, days until first fever, days of anti-fungal therapy given, hospitalization days, days of trial medication use, use of chlorhexidine baths (yes or no), use of prophylactic CVL locks (ethanol or antibiotic locks for bacteremia prophylaxis) (yes or no) and the name and start/stop dates for any oral and parenteral antibacterial therapy. Incidence of sepsis and severe bacterial and fungal microbiologically documented infections and clinically documented infections (CTCAE version 4, Grade 4 and Grade 5) will be recorded. For patients who die during the infection observation period and who have an autopsy performed, the report of the autopsy will be requested.

#### 7.1.2.2 Sterile Site Cultures

Patients will have sterile site bacterial isolate data collected during the infection observation period. Sterile site cultures will be done as part of good patient care, for example blood cultures obtained in patients with new fevers. Decisions about what types of culture and when the cultures are drawn will be made according to local institutional practice.

Bacteria isolated from sterile site cultures will be processed at the microbiology labs at the local institutions caring for the patient. The final laboratory report for each bacterial isolate (including the bacteria name, date the culture was obtained, culture source, and antibacterial resistance profile) will be submitted via the document imaging system for central review. A panel of 4 committee members will centrally review all positive sterile site cultures and antibacterial resistance profiles. It is anticipated that the techniques for establishing an isolate's minimum inhibitory concentration (MIC) will vary between institutions. However, this variability should not have great impact on whether organisms are classified as resistant.

## 7.1.2.3 Clostridium difficile Associated Diarrhea

Data to be collected for CDAD will include positive *C. difficile* toxin assay results, date of the sample and if Grade 2 or higher (CTCAE version 4) diarrhea was present on the date of *C. difficile* positive toxin sampling.

## 7.1.2.4 Invasive Fungal Infections

Data to be collected for IFI will be limited to whether or not there was a culture or pathologically documented IFI and fungal name, and the source of the culture or pathology, if available, during the infection observation period.

#### 7.1.3 Musculoskeletal Assessment

Evaluation for pre-defined musculoskeletal disorders will be collected at baseline and then in the late MSK monitoring period 2 and 12 months post-completion of the infection observation period (see Section 7.1.2 for definition). This evaluation will be done for all patients (i.e., Arms A and B). A window of +/- 2 weeks of the specific timepoint for the 2 and 12 month assessments is allowed to accommodate patient scheduling. The individual performing this evaluation will be assigned by the local institution and will be blinded to the patient's assigned study arm (whether or not they received levofloxacin). The individual performing the evaluation does not have to be a physician or an oncologist but must in the judgment of the institutional PI have the clinical skills to perform the assessment. Attribution of the

etiology of any musculoskeletal signs or symptoms will be made by the blinded assessor. The Musculoskeletal Data Form will be used for assessment at these timepoints (see Appendix I). The objective evaluation criteria for the musculoskeletal adverse events include:

- i. Tendinopathy: inflammation or rupture of the tendon by physical exam or MRI
- ii. Arthritis: inflammation of the joint evidenced by redness or swelling
- iii. Arthralgia: complaint of pain in the joint (specifically the joint)
- iv. Gait abnormality: limping or refusal to walk

It is anticipated that the etiologies for the musculoskeletal signs and symptoms for some patients may include steroid myopathy, vincristine neuropathy, avascular necrosis, fracture, tumor-related pain and filgrastim-related pain. If upon evaluation a patient is found to have evidence of new musculoskeletal toxicity that is not otherwise explained, it is suggested that the patient be referred to the appropriate specialist (e.g., pediatric rheumatologist or orthopedic surgeon) for further evaluation.

In addition to the baseline, 2 and 12 month assessments, monitoring for any patient with signs or symptoms suggestive of tendinopathy (tendonitis or tendon rupture) will be done. For any patient on Arm B with tendonitis or tendon rupture, levofloxacin will be discontinued immediately.

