In contrast to the issue of tendinopathy, the use of fluoroquinolones in pediatrics has been limited by concerns for the potential risk of arthropathy. In juvenile animals, exposure to fluoroquinolones has been associated with a risk of arthropathy expressed clinically as lameness and with characteristic histologic findings including blisters and erosions of articular cartilage. There is, however, a significant body of evidence supporting the effectiveness and safety of quinolone antibiotics, including levofloxacin, in the pediatric population. Ciprofloxacin is licensed by the FDA for specific clinical situations in individuals < 18 years of age. A recent report on the safety profile of levofloxacin in children, which included more than 2,500 subjects, found that the incidence of musculoskeletal disorders (primarily arthralgia) was significantly higher in levofloxacin-treated patients (3.4% versus 1.8%, p=0.025 at 1 year post-exposure). However, this estimate was based on reporting from non-blinded parents and thus may have been biased. In addition, the quality of the musculoskeletal disorder in the levofloxacin-treated and comparator groups did not appear to be different. Given the rare occurrence of these side effects and questionable attribution to levofloxacin, the continued evaluation of levofloxacin prophylaxis in specific high-risk pediatric populations in controlled research settings is justifiable.

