# 2.5 **Summary**

Bacterial infections continue to be a leading cause of morbidity and toxic death in children receiving treatment for AML, relapsed ALL and for those undergoing HSCT. Data from adult studies suggest that antibiotic prophylaxis decreases the incidence of infection-related death in patients receiving intensive myelosuppressive therapy; however, antibiotic prophylaxis in pediatric patients is largely unstudied. This open-label, randomized, controlled trial will evaluate whether prophylactic therapy with levofloxacin will decrease the incidence of bacteremia in pediatric patients being treated with intensive chemotherapy for AL or for those undergoing HSCT. In addition, the study design will allow assessment of the potential risks of prophylactic therapy such as quinolone-related musculoskeletal side effects. The ancillary study within this trial represents a unique opportunity to establish the potential of increased risk of evolution of resistance and persistence of resistance among gastrointestinal colonizing organisms frequently associated with invasive bacterial infection. Such data are necessary to judge the balance between the risks and benefits of antibiotic prophylaxis and thus help determine whether prophylactic levofloxacin should be incorporated in clinical care of children and young adults at high risk for serious infections secondary to cancer therapy.

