## 4.0 TREATMENT PLAN

## 4.1 **Overview of Treatment plan**

Timing of protocol therapy administration, response assessment studies, and surgical interventions are based on schedules derived from the experimental design or on established standards of care. Minor unavoidable departures (up to 72 hours) from protocol directed therapy and/or disease evaluations (and up to 1 week for surgery) for valid clinical, patient and family logistical, or facility, procedure and/or anesthesia scheduling issues are acceptable per COG administrative Policy 5.14 (except where explicitly prohibited within the protocol).

In this study, patients will be randomized to no levofloxacin (Arm A) or levofloxacin (Arm B) at time of enrollment. Patients in Arm A receive no protocol treatment. Patients in Arm B receive levofloxacin as detailed below.

The required observations and adverse event reporting are identical in the two arms. See Section 7 for required observations and Section 11 for Adverse Event reporting.

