For the secondary endpoints, the total number of days of parenteral antibiotic administration will be compared between the 2 arms using 2-sample t-test. Wilcoxon rank sum test will also be considered. We will also use linear regression models to estimate any treatment difference in total days of parenteral antibiotic administration and adjust for randomization stratification and potentially other patient or treatment characteristics. The incidence of febrile neutropenia, severe infection from bacteremia, fatal infections from bacteremia and musculoskeletal adverse events will be compared between the 2 randomized arms similarly as the analyses on bacteremia. For the analysis on the incidence of tendon rupture, we will also consider separating levofloxacin patients into those with/without concurrent steroid use and comparing them separately to control patients, or adjusting for concurrent steroid use as covariate in logistic regression models. The incidence of CDAD and proven or probable IFIs will also be compared between the 2 study arms in a similar manner. A patient with multiple documented episodes of CDAD or proven or probable IFI will only be counted once when calculating the binary incidence rates. For these secondary endpoints, appropriate regression models that combine AL and HSCT patients will be performed to evaluate the treatment effect with levofloxacin in the two patient groups; test for interaction between treatment and patient group will be performed to examine if the effect of levofloxacin on these secondary endpoints differs between the two patient groups.

Factors that can potentially confound the true association of the randomized exposure (levofloxacin) with the primary and two of the secondary outcome measures (1.2.1 and 1.2.2) will be compared across the two randomization arms to assure a balanced distribution. These include the use of antibiotic or ethanol as dwells or locks in central venous catheters (CVC) to reduce CVC infections and the use of chlorhexidine gluconate baths to reduce CVC infections. Analyses adjusting for these factors will be exploratory in nature.

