## 9.3.4 Interim Monitoring

Interim efficacy monitoring on the incidence of bacteremia will be performed twice when data is available for approximately one-third and two-thirds of patients (separately for AL patients and HSCT patients). Monitoring boundary will be based on Lan-Demet's method with spending function  $\alpha t^2$ . Futility analyses based on conditional power will also be performed at the same time separately for each patient group. The probability of establishing efficacy of levofloxacin given the currently observed data will be calculated. In calculating the conditional power, the outcome for future patients will be assumed to follow the alternative hypothesis. If the conditional power falls below 10%, it will be considered evidence that it is unlikely to establish efficacy of levofloxacin in the particular patient group at the end of the study. The data will be referred to the COG Data Safety and Monitoring Committee (DSMC) for consideration of early termination for the particular patient group. Accrual will not be suspended for these interim monitoring and analyses. The incidence of musculoskeletal disorder will be monitored between the 2 arms by descriptive statistics and Fisher's exact test at each interim DSMC report, which occurs approximately every 6 months during the first 2 years and annually thereafter. For tendon rupture, as concurrent steroid use is considered a risk factor, the analysis will also be considered separately for levofloxacin patients with/without concurrent steroid use or with adjustment for steroid use. A previous report on > 2,500 patients found a small increase in the musculoskeletal disorder incidence (3.4% versus

1.8%) in levofloxacin treated patients; however our study is not powered to detect a difference of this magnitude. Therefore, the monitoring on incidence of musculoskeletal disorder will be informal and mainly for safety reassurance. Such safety monitoring will always be done at marginal alpha level of 0.05 and not adjusted for the multiple comparisons. If any such safety comparison suggests a significantly higher incidence of musculoskeletal disorder for levofloxacin, the study committee will carry out a review of the observed disorders; the results and any committee recommendation will be reported to the DSMC. The DSMC may also have its own assessment and recommendation about musculoskeletal event safety given the observed data.

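### Arthralgia is a complaint from families who know the arm, yet the plan calls it objective and does not compare it separately from signs found by the blinded assessor

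*Combined protocol and SAP*

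**What the plan says.** Section 7.1.3 has musculoskeletal status assessed in both arms at baseline and at 2 and 12 months after the infection observation period. The assessor "will be blinded to the patient's assigned study arm (whether or not they received levofloxacin" and also attributes the cause of any sign or symptom.

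The list of four disorders opens with "The objective evaluation criteria for the musculoskeletal adverse events include". Tendinopathy rests on physical examination or MRI, and arthritis on redness or swelling. Gait abnormality is a limp or refusal to walk. The remaining item is "Arthralgia: complaint of pain in the joint (specifically the joint", which needs no finding on examination.

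Patients and families are not masked. Section 2.5 says "This open-label, randomized, controlled trial will evaluate whether prophylactic therapy with levofloxacin will decrease the incidence of bacteremia in pediatric patients", and section 4.1 says "Patients in Arm A receive no protocol treatment".

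Section 2.3 cites a report of more than 2,500 children with musculoskeletal disorders, mainly arthralgia, in 3.4% on levofloxacin and 1.8% on the comparator. It cautions that "this estimate was based on reporting from non-blinded parents and thus may have been biased".

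For the final analysis, 9.3.3 says "musculoskeletal adverse events will be compared between the 2 randomized arms similarly as the analyses on bacteremia". For monitoring, 9.3.4 says "The incidence of musculoskeletal disorder will be monitored between the 2 arms by descriptive statistics and Fisher's exact test at each interim DSMC report", at a level of 0.05 each time without adjustment. A significant levofloxacin excess leads to a study committee review and a report to the DSMC. Only tendon rupture has further analysis of its own, for steroid use.

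**The concern.** A blinded assessor who writes down a complaint does not mask the person complaining. Parents who know that their child took a quinolone, and who have been told of joint effects, may mention joint pain more readily than parents of untreated children. The protocol itself gives this mechanism as a reason for caution about the earlier result, and arthralgia was the main component of that result.

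The plan neither separates arthralgia from the examined signs nor says how the four disorders form the compared outcome. If the levofloxacin arm shows an excess, the planned comparisons will not tell whether it rests on signs seen by a masked examiner or on unmasked complaints. The excess could then be discounted by the argument in section 2.3, and the trial would have no pre-specified result with which to answer. Musculoskeletal safety is a named secondary objective (1.2.4), so this should be settled before the data are seen.

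**Working it through.** **1. The plan's own statement on power.** Section 9.3.4 says that the study is not powered for 3.4% against 1.8%. With a pooled-variance Chi-square test (two-sided 0.05, 1:1), power is 12.7% at 133 per arm, 17.0% at 200 and 25.4% at 333. With Fisher's exact test it is 5.0%, 9.4% and 18.5%. Reaching 80% by Chi-square would take 1,552 per arm. The statement is correct.

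**2. What is masked.**

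| Disorder | Basis in 7.1.3 | Source masked to arm? |
|---|---|---|
| Tendinopathy | examination or MRI | yes, through the assessor |
| Arthritis | redness or swelling | yes, through the assessor |
| Gait abnormality | limp or refusal to walk | if observed by the assessor |
| Arthralgia | complaint of pain | no |

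**3. How far differential reporting could move the test.**

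From the documents:
- 133 AL and 200 HSCT patients per arm (9.3.2), 333 per arm together (9.5.3.1);
- Fisher's exact test at 0.05 (9.3.4), taken here as two-sided;
- the earlier comparator rate of 1.8% (2.3).

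Assumed, because the documents give no value:
- no true drug effect;
- a control prevalence p of 10% as an alternative to 1.8%, which comes from another population;
- a reporting ratio r of 1, 1.25 or 1.5 in the levofloxacin arm.

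Let X ~ Bin(n, p) be the count in the control arm and Y ~ Bin(n, r·p) the count in the levofloxacin arm. The quantity wanted is

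P(signal) = Σ P(X = x)·P(Y = y), over all pairs with y > x and Fisher p ≤ 0.05.

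The levofloxacin rates r·p are 1.8%, 2.25% and 2.7% for p = 1.8%, and 10%, 12.5% and 15% for p = 10%. Exact enumeration gives:

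| Per arm | Control prevalence | r = 1 | r = 1.25 | r = 1.5 |
|---|---|---|---|---|
| 333 | 1.8% | 1.2% | 3.3% | 7.4% |
| 333 | 10% | 1.8% | 14.5% | 45.4% |
| 200 | 10% | 1.7% | 9.2% | 27.6% |
| 133 | 10% | 1.5% | 6.6% | 18.3% |

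**4. Inflating the complaint only.** Step 3 applies r to the whole outcome. Suppose instead that examined signs occur in 2% of both arms, independently of complaints, and that 10% of controls complain (both assumed). The any-disorder rate is then 1 − 0.98 × 0.90 = 11.8% in controls and, at r = 1.5, 1 − 0.98 × 0.85 = 16.7% on levofloxacin. P(signal) is 16%, 24% and 40% at 133, 200 and 333 per arm. A test of the examined signs alone signals in 0.5%, 0.9% and 1.2%, because reporting does not reach it.

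**The case against.** **The plan has real safeguards.** The assessor is blinded and attributes cause while blinded. Appendix I asks only about the day of assessment, locates each joint and offers a list of alternative diagnoses. This stands: assessor bias is removed and recall bias is limited. A reader might infer that the earlier study's bias carries over whole, and the documents do not support that. What remains is reporter bias in arthralgia, and perhaps in refusal to walk. Attribution does not clearly remove it, because 9.3.3 and 9.3.4 do not say that attributed cause decides which events are compared.

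**No composite is defined.** A reader might infer that the four disorders are pooled into one any-of-four outcome. That is a natural reading of an incidence of musculoskeletal disorder, but no section says so, and Appendix I gives each disorder its own box. The supportable statement is that the plan does not say how the components are combined or separated.

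**Section 2.3 does not rest on parental reporting alone.** It says only that bias was possible. It adds that the disorders looked similar in quality between groups, and it also cites rarity and doubtful attribution. This stands, so reporter bias is one ground among several.

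**The consequence is limited.** Section 9.3.4 calls the monitoring informal. A signal leads to a review, in which the separate boxes can be seen, and not to stopping. This also stands. It limits the harm at interim looks but does not supply the missing comparison at the final analysis.

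**Arthralgia should stay in the trigger.** It was the main component of the earlier signal. Removing it would cost sensitivity in a comparison that already has little power, so the fix below does not remove it.

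**Conclusion.** The point holds as a gap in labelling and analysis. A complaint from unmasked reporters is called objective, and no planned comparison separates it from signs found by the masked assessor.

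The size is uncertain. At 333 per arm with families reporting 1.25 to 1.5 times as often, a false levofloxacin signal at a single test arises in about 3–7% of trials at 1.8% control prevalence and 15–45% at 10%. At 10% the range is 7–18% with 133 per arm and 9–28% with 200 per arm. Without reporting bias it is about 1–2%, and lower in the smaller groups when prevalence is low.

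These figures rest on assumed prevalence, reporting ratio and direction of bias. Nothing in the documents shows that differential reporting will occur here, so they show sensitivity and are not a forecast. The 333-per-arm figures are the top of the range for a given prevalence, because 9.3.3 runs the bacteremia analyses separately for AL and HSCT and 9.3.4 does not say whether the interim safety test is split. A reader might infer that the musculoskeletal comparison is invalid. The documents do not support that: three of the four disorders can be recorded by a masked examiner.

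**What to change.** - **Sections 9.3.3 and 9.3.4.** Keep the overall musculoskeletal comparison and the review trigger, and state how the overall outcome is formed. Add two component comparisons from the existing Appendix I boxes: (a) signs found on examination by the blinded assessor, namely tendinopathy, arthritis, and gait abnormality when the assessor observes it; (b) arthralgia, labelled as reported by patient or parent and unmasked. State in advance that an excess confined to (b) is open to reporting bias.
- **Section 7.1.3.** Stop describing arthralgia as objective.
- **Appendix I.** Add a line asking families not to tell the assessor the arm. This protects the assessor's blinding; it does not cure reporter bias, which is why (b) needs its label.

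The cost is text in 7.1.3, 9.3.3, 9.3.4 and Appendix I. No visits or patients are added. The form may need a mark to show whether a gait abnormality was observed or only reported. The examined-sign comparison will have few events and low power, so a null result there will reassure only weakly. It also adds to the unadjusted safety comparisons, which is acceptable for monitoring that the plan already describes as informal.
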